3.6 Patient Eligibility

3.6.1 Inclusion Criteria

Critically ill children admitted to the PICU are eligible for enrollment if they are:

- between 37 weeks post-conceptional age and less than 18 years; AND
- receiving ventilatory assistance through an endotracheal tube or a tracheostomy; AND
- receiving fentanyl or morphine infusion for analgesia or sedation.

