3.7 Inclusion of Women and Minorities

The gender, ethnic and racial composition of patients enrolled in all CPC-CRN studies is a function of the characteristics of patient populations at each Clinical Center selected by the National Institute for Child Health and Human Development (NICHD) to participate in the network. During this study, the Data Coordinating Center (DCC) will monitor patient accrual by race, ethnicity, and gender. If necessary, additional recruitment efforts will be made at specific centers to ensure that the aggregate patient sample contains appropriate gender and minority subsets.

4 Data Management

Research data will be collected at the time of enrollment and daily data collection will continue until the last dose of opioids, or a total of 14 days after enrollment, or the patient's death or PICU discharge, whichever occurs first.

This protocol includes a detailed list of data elements to be collected, and if data elements are added or subtracted from this, a protocol amendment will be produced. However, specific choice sets for these data may be amended without being considered a change to this protocol. The choice sets that are listed in the protocol are intended to help the reader completely understand the intent of the data element and to assist implementation of the electronic data collection system by the CPCCRN DCC.

Data will be entered into an electronic data collection system to be designed and implemented by the CPCCRN DCC. The Study Coordinator may choose to print hard copy forms to use as worksheets. If used, the paper worksheets should be retained at the clinical center in a locked file cabinet within a locked office until the study is complete and all CPCCRN publications associated with MOTIF have been accomplished.

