4.1 Definitions

- **Analgesia:** the reduction or absence of the sense of pain without loss of consciousness, as reported by the patient, or judged clinically from the patients behavior or physiological responses
- **Sedation:** a pharmacologically produced depressed level of consciousness associated with reduced anxiety, stress, and excitement

- First study day: the period from the time that the initial dose of opioid is received in the PICU up to 23:59 hours on that day
- **Subsequent study days:** each calendar day starting at midnight (00:00 hours) and ending at 23:59 hours after the completion of the first study day (as defined above) during which the enrolled subject is an inpatient in the PICU
- **Ventilated day:** PICU day during any part of which the child requires mechanical ventilation support greater than chronic baseline requirements (out of the hospital), provided by endotracheal tube, tracheostomy, laryngeal or face mask
- **Invasive procedure:** Any procedure that breaks the skin barrier or mucous membrane barrier or involves the placement of a medical device (catheter, probe, electrode, drain, prosthetic, or anything else) into a body orifice or body cavity, other than momentary suctioning of the nose, mouth, endotracheal tube, or tracheostomy tube.
- **Opioid tolerance:** the need for increasing doses of opioid drugs in order to maintain the same pharmacological effects as those seen at the initiation of therapy. For the purposes of this study, opioid tolerance is clinically defined as a doubling of the total daily opioid dose (including infusions and boluses) as compared to the total daily opioid dose required during the first 24 hours of opioid therapy, in order to maintain adequate analgesia and sedation
- **Regularly scheduled opioids:** the subject receives opioid drugs daily, given at regularly scheduled intervals. In response to specific symptoms or signs, if the subject has received more than one opioid dose per day, on more than three days during the past week, or a total of more than six opioid doses in the past one week, then they will be considered equivalent to those receiving regularly scheduled opioids.
- **Chronic opioid treatment:** if the subject has received scheduled regular opioids (as defined above) for more than one week, they will be classified as receiving chronic opioid treatment.

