- Chromosomal abnormality
- Diabetes
- Drug overdose (e.g. ingestion, toxicity)
- Gastroesophageal reflux
- Cardiovascular disease acquired
- Cardiovascular disease congenital
- HIV infection
- Hypoxic-ischemic encephalopathy of recent onset (acute, not static)
- Medical device malfunction
- Meningitis
- Pneumonia / bronchiolitis
- Seizures (includes complications of seizure therapy)
- Sepsis
- Shock
- Suicide attempt (includes intentional drug overdose)
- Transplant
- Trauma
- Other Diagnosis
- 17. Chronic Diagnoses (Select Multiple)
 - Bronchopulmonary dysplasia (BPD)
 - Cancer
 - Cerebral palsy
 - Chromosomal abnormality
 - Congenital heart disease
 - Diabetes
 - HIV infection
 - Hydrocephalus
 - Intraventricular hemorrhage (from perinatal period)
 - Mental retardation

- Meningomyelocele / spina bifida
- Short gut syndrome
- Static encephalopathy
- Transplant
- Other Diagnosis
- 18. Postoperative Surgical Status (Select one)
 - Not postoperative
 - Postoperative
 - Cardiac surgery
 - Neurosurgery
 - Transplant surgery
 - Trauma surgery
 - Other surgery
- 19. Date and time of start of mechanical ventilation via endotracheal tube or tracheostomy during current hospital admission
- 20. Date and time of first morphine or fentanyl dose in the PICU this is defined as Time 0 for the baseline opioid dose
- 21. Total amount of morphine or fentanyl (mg/kg) given before midnight on the first study day (total amounts of drug infusions plus additional boluses of morphine or fentanyl)
- 22. Total amount of midazolam or lorazepam (mg/kg) given before midnight on the first study day (total amounts of drug infusions plus additional boluses of midazolam or lorazepam.
- 23. Other sedative (Table 1 on the following page) or analgesic (Table 2 on page 23) agents used during the first study day. If drug combinations are used, record all components of the drug combination.

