4.3 Subsequent Daily Data Elements

Study Day One is the day of enrollment, beginning at the time of the first morphine or fentanyl administration in the PICU, and ending at 23:59 on that day. Each subsequent study day is defined as midnight (00:00) to 23:59. On each subsequent day (not study day one), the following data elements

Sedative Drugs and Components Sedative Drugs Answer Ketamine Yes or No Propofol Yes or No Chloral hydrate Yes or No Chlorpheniramine Yes or No Clonazepam Yes or No Diazepam Yes or No Droperidol Yes or No Etomidate Yes or No Yes or No Haloperidol Yes or No Hydroxyzine Methohexital Yes or No Yes or No Pentobarbital Phenobarbital Yes or No Promethazine Yes or No Yes or No Thiopental Yes or No Other (specify)

Table 1: Sedative agents.

Analgesic Drugs and	Components
Analgesic Drugs	Answer
Dexmedetomidine	Yes or No
Acetaminophen	Yes or No
Ibuprofen	Yes or No
Acetylsalicylic acid	Yes or No
Alfentanil	Yes or No
Buprenorphine	Yes or No
Butorphanol	Yes or No
Clonidine	Yes or No
Codeine	Yes or No
Dextromethorphan	Yes or No
Hydromorphone	Yes or No
Ketorolac	Yes or No
Meperidine	Yes or No
Methadone	Yes or No
Nalbuphine	Yes or No
Oxymorphone	Yes or No
Remifentanil	Yes or No
Tramadol	Yes or No
Other (specify)	Yes or No

Analgesic Drugs and Components

Table 2: Analgesic agents.

will be collected. This daily data collection will continue through Study Day 14, discontinuation of opioid therapy, death, or PICU discharge, whichever occurs earliest.

- 1. Date of data collection
- 2. Study day number (2 to 14)
- 3. Weight (kg) last measured or estimated weight
- 4. Was morphine or fentanyl infusion weaned (decreased) in the past 24 hours? (Yes or No)
- Was morphine or fentanyl infusion discontinued in the past 24 hours? (Yes or No) If yes to this question,
 - (a) Was morphine or fentanyl infusion restarted in the past 24 hours? (Yes or No)
 - (b) Were intermittent opioid doses started in the past 24 hours? (Yes or No)
- 6. Were muscle relaxants used in the past 24 hours? (Yes or No)
- 7. Were physical restraints used in the past 24 hours? (Yes or No)
- 8. Did inadvertent or unplanned dislodgement of an endotracheal tube occur in the past 24 hours? (Yes or No)
- 9. Did inadvertent or unplanned dislodgement of a central venous line occur in the past 24 hours? (Yes or No)
- 10. Did inadvertent or unplanned dislodgement of an arterial line occur in the past 24 hours? (Yes or No)

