5.1 Analysis of Primary Endpoint

The primary endpoint for the MOTIF Study is the incidence of opioid tolerance among PICU patients receiving morphine or fentanyl infusions for analgesia and sedation. For the purposes of this study, opioid tolerance is defined by a doubling of the total daily opioid dose from the initiation of opioid therapy (0-24 hours) in the PICU. Tolerance can develop at any time during opioid therapy; therefore, as would be the case for an intention-to-treat analysis in a clinical trial, subjects who die or are discharged from the PICU will be included in the denominator for this endpoint, irrespective of number of days in PICU prior to death or discharge. We will examine the incidence of this endpoint 7 days and 14 days after initiation of morphine or fentanyl infusion therapy, in order to help determine appropriate parameters for future clinical trials. Rates of the primary endpoint will be summarized as proportions achieving tolerance by 7 days and by 14 days after opioid therapy initiation, together with appropriate confidence intervals.

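### The primary endpoint has no single time origin, so when an intermittent opioid dose precedes the infusion, an unchanged infusion can be scored as tolerance

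*Protocol*

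**What the plan says.** The protocol attaches the primary endpoint to several starting points.

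- **First dose.** Section 4.2, item 20, records the first morphine or fentanyl dose in the PICU and states that "this is defined as Time 0 for the baseline opioid dose". Section 4.1 defines the first study day as "the period from the time that the initial dose of opioid is received in the PICU up to 23:59 hours on that day". Neither requires that dose to be an infusion.
- **Baseline window.** The tolerance definition in section 4.1 looks for a doubling of the daily total, infusions and boluses together, "as compared to the total daily opioid dose required during the first 24 hours of opioid therapy".
- **Infusion.** Section 3.6.1 (and 1.6.1) admits a ventilated child only when "receiving fentanyl or morphine infusion for analgesia or sedation".
- **Analysis clock.** Section 5.1 examines the endpoint "7 days and 14 days after initiation of morphine or fentanyl infusion therapy". Its next sentence reports the same proportions counted from the start of opioid therapy.
- **Enrolment.** The opening of section 4 says that "daily data collection will continue until the last dose of opioids, or a total of 14 days after enrollment". Section 4.3 says "Study Day One is the day of enrollment, beginning at the time of the first morphine or fentanyl administration in the PICU".

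The dose data are calendar totals that pool infusion and bolus: up to midnight on day one (4.2, item 21) and midnight to midnight afterwards (4.3, item 15). No element in sections 4.2 to 4.4 records when the infusion started.

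**The concern.** These origins coincide only if the first opioid in the PICU is the qualifying infusion and the child is enrolled that day. No criterion requires this. The exclusion for prior scheduled opioids concerns only the time before PICU admission.

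A child may receive an intermittent dose first and become eligible later, once ventilated and on an infusion. The baseline then contains the bolus and little or none of the infusion, and simply starting the infusion may satisfy the doubling rule. The error runs one way, towards more tolerance, and a larger sample does not shrink it. Section 5.4 intends these incidence estimates to inform the sample size of an intervention trial.

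The follow-up clock is affected as well. If enrolment falls g days after the first PICU opioid, 14 days after enrolment is 14 + g days after initiation.

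**Working it through.** **1. The plan's own figures.** Section 5.4 gives N = 450 and a precision of 4-5%. The 95% half-width is 1.96 × √(p(1 − p)/450):

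- p = 0.25 (the outcome rate assumed in 5.4): 4.0%
- p = 0.40: 4.5%
- p = 0.50: 4.6%

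The stated precision is reproduced.

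**2. Notation.** The infusion runs at a constant rate. The bolus at Time 0 is worth b hours of that infusion (assumed; the protocol gives no value). The infusion starts t hours later. A full infusion day is 24 hours' worth of drug, and tolerance is scored at a ratio of 2 or more.

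**3. The 24-hour baseline of section 4.1.** For t up to 24, ratio = 24/(b + 24 − t). This reaches 2 when t ≥ 12 + b, that is 12.5, 13 or 14 hours for b = 0.5, 1 or 2. With b = 1:

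| t (h) | 2 | 6 | 12 | 13 | 18 | 24 |
|---|---|---|---|---|---|---|
| ratio | 1.04 | 1.26 | 1.85 | 2.00 | 3.43 | 24 |

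A bolus shortly before the infusion does no harm here.

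**4. The pre-midnight total of section 4.2, item 21.** With W hours from Time 0 to midnight, ratio = 24/(b + max(W − t, 0)). If the bolus falls on an earlier calendar day than the infusion, t ≥ W and the ratio is 24/b: 24 for b = 1, and still 24/11 = 2.18 for b = 11. Any b below about 12 is scored on the first full infusion day.

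**5. One child, three baselines.** Bolus worth 1 hour at 22:00, infusion from 02:00 the next day, rate unchanged:

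- 24 hours from the bolus: 24/(1 + 20) = 1.14, not scored
- bolus to midnight: 24/1 = 24, scored
- 24 hours from infusion start: 24/24 = 1.0, not scored

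**6. What belongs to the midnight cut alone.** An infusion with no earlier bolus, started 12, 6 or 2 hours before midnight, gives 24/12 = 2.0, 24/6 = 4.0 and 24/2 = 12.0. When bolus and infusion share a calendar day, the bolus adds to the baseline. With W = 12, t = 4 and b = 1 the ratio is 24/9 = 2.67, against 24/8 = 3.0 if counting starts at the infusion. The choice of first dose as origin therefore adds false doublings under this cut only when the bolus falls on an earlier calendar day.

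**7. Effect on the estimate.** If a share f of truly non-tolerant children is falsely scored, observed incidence = p + (1 − p)f. At p = 0.25, assumed values of f = 2%, 5%, 10% and 20% add 1.5, 3.75, 7.5 and 15 points. The shift equals the 4-point half-width at f = 0.04/0.75 = 5.3%. At p = 0.50, matching the 4.6-point half-width needs f = 0.046/0.50 = 9.2%.

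**The case against.** The best defence is that the protocol has a prevailing origin. The abstract, sections 1.3 and 3.3, and most of 5.1 count from the start of opioid therapy, and only one clause of 5.1 departs from this. Measuring tolerance from first exposure is a defensible choice. Section 4.3 also places enrolment and first administration on the same day, and a consent waiver removes one common cause of late enrolment.

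Much of this stands. It means that 5.1 contradicts itself; a reader might infer that the 7- and 14-day analysis is simply tied to the infusion, and the text does not support that. But same-day enrolment is asserted in 4.3 and enforced nowhere, and the prevailing origin still does not say how a bolus-only baseline is handled.

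A reader might also infer that every child with a bolus on an earlier day is a false positive. Under section 4.1 that is wrong: the 22:00 bolus above gives 1.14. It comes close to true only under the midnight total, and then only for a child with a full infusion day and a bolus worth less than about 12 hours of infusion.

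The definition's reference to keeping analgesia and sedation adequate might seem to screen out such cases. No pain or sedation score is collected, so it cannot be applied. A later analysis plan cannot repair this either. Enrolment and first-dose dates are recorded, so that lag is recoverable, but neither the infusion start nor a 24-hour baseline can be rebuilt from pooled calendar totals.

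**Conclusion.** The concern holds in a conditional form. The protocol uses inconsistent origins for its primary endpoint and sets no limit on the gap between first PICU opioid and enrolment. The data it collects allow an unchanged infusion to count as a doubling. Under the stated 24-hour baseline this needs a gap of about 12 hours plus the bolus equivalent. Under the total actually collected it needs only a bolus on an earlier calendar day worth less than about 12 hours of infusion.

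The size is unknown, because the protocol does not say how often or how long an intermittent dose precedes the infusion. The firm statement is the break-even: at a true 25%, about 5% of non-tolerant children falsely scored shifts the incidence by about 4 points. That calculation assumes a constant infusion rate and takes 25% from section 5.4. A reader might go further and quote a specific inflated incidence, or claim that late enrolment over-represents long stays. The document has no figure for either.

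This should be settled before enrolment, since the missing times and doses cannot be recovered from the planned data afterwards.

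**What to change.** - Choose one origin for baseline, Study Day One, the 14-day limit and the 7- and 14-day proportions, for example the start of the qualifying infusion while ventilated. Reconcile sections 4, 4.1, 4.2 (items 20 and 21), 4.3 and 5.1 with it.
- State how opioid given before that origin is treated.
- Record the date and time of both the first PICU opioid and the infusion start.
- Collect the baseline dose over the full 24 hours from the chosen origin. Moving the origin while keeping the midnight cut is not enough: an unchanged infusion started 12 hours or less before midnight would still be scored.
- Report, as a sensitivity analysis, the incidence excluding children whose first opioid preceded the infusion.

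The cost is a protocol amendment, one extra date/time field and one 24-hour dose field. An enrolment window or left truncation at enrolment is optional; a window would lose some children identified late.

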- 11. Did inadvertent or unplanned dislodgement of a thoracostomy tube occur in the past 24 hours? (Yes or No)
- 12. Did inadvertent or unplanned dislodgement of a peripheral venous line occur in the past 24 hours? (Yes or No)
- 13. Did inadvertent or unplanned dislodgement of a surgical drain occur in the past 24 hours? (Yes or No)

- 14. Did inadvertent or unplanned dislodgement of a urinary catheter occur in the past 24 hours? (Yes or No)
- 15. Total amount of morphine or fentanyl (mg/kg) given on this study day (total amounts of drug infusion plus additional boluses, from 00:00 to 23:59 hours)
- 16. Peak hourly dose of fentanyl or morphine given during the 24 hour day $(\mu g/kg/hr)$
- 17. If the subject is receiving midazolam by continuous IV infusion,
 - Number of hours that the midazolam drip was continued in the 24 hour day
 - Highest hourly dose (mg/kg) for midazolam given during the 24 hour day
- 18. If the subject is receiving intermittent lorazepam (by any route), total dose (mg/kg) given during the 24 hour day
- 19. Identify all other sedative (Table 1 on page 22) or analgesic (Table 2 on page 23) agents used during the first study day. If drug combinations are used, record all components of the drug combination.
- 20. Did the subject undergo a surgical procedure during this 24 hour period? Yes or no
- 21. If the subject did undergo a surgical procedure, select the category:
 - Cardiac surgery
 - Neurosurgery
 - Transplant surgery
 - Trauma surgery
 - Other surgery
- 22. Did the subject undergo any invasive procedures during this 24 hour period? Yes or no
- 23. If yes, how many procedures?
- 24. Did the subject have a creatinine > 1.2 during this 24 hour period? Yes or no

- 25. If yes, is the patient requiring dialysis or continuous renal replacement therapy? Yes or no
- 26. Did the subject have hepatic dysfunction associated with an INR > 2.0 during this 24 hour period? Yes or no

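### The primary endpoint is defined against the dose in the first 24 hours, but the listed data stop the Day 1 total at midnight and no scaling rule is given

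*Protocol*

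**What the plan says.** Section 5.1 (repeating 1.3 and 3.3) defines the endpoint as a "doubling of the total daily opioid dose from the initiation of opioid therapy (0-24 hours) in the PICU". Section 4.1 gives the same comparator, a later daily total "as compared to the total daily opioid dose required during the first 24 hours of opioid therapy", and counts both infusions and boluses.

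The data elements use different windows:

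- **First study day (4.1):** "the period from the time that the initial dose of opioid is received in the PICU up to 23:59 hours on that day".
- **Start time (4.2, item 20):** the date and time of the first morphine or fentanyl dose in the PICU; "this is defined as Time 0 for the baseline opioid dose".
- **Day 1 dose (4.2, item 21):** "Total amount of morphine or fentanyl (mg/kg) given before midnight on the first study day".
- **Later days (4.3):** "Each subsequent study day is defined as midnight (00:00) to 23:59". Item 15 collects "Total amount of morphine or fentanyl (mg/kg) given on this study day (total amounts of drug infusion plus additional boluses, from 00:00 to 23:59 hours".

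No section says how the Day 1 amount becomes a 24-hour baseline.

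**The concern.** The definition needs the dose over hours 0 to 24. That period nearly always crosses midnight. The part after midnight is contained in the Day 2 calendar total and is not recorded separately, so the defined baseline cannot be computed exactly from the listed elements. The baseline amount that is on file covers a part-day whose length depends only on the clock time of the first dose, while every comparator is a whole day.

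The incidence of tolerance is Specific Aim 1, and Section 5.4 intends it to inform the sample size of an intervention trial. A baseline whose length varies with start time could raise the estimate by far more than its planned precision. It would also let any factor associated with start time look like a risk factor in the Section 5.3 models. If a part-day were treated as a whole day, average daily dose (5.2) and the repeated-measures dose trajectories (5.3) would show an artificial rise from Day 1 to Day 2.

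**Working it through.** **The plan's own figure.** Section 5.4 gives a 95% confidence interval precision of 4-5% with 450 subjects. Half-width = 1.96 × √(p(1−p)/450):

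- p = 0.25 (the outcome rate assumed in 5.4): 4.0 points
- p = 0.50: 4.6 points

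The stated figure reproduces and is the yardstick below.

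**Ratio at a constant rate.** Let t be the clock hour of the first dose. The Day 1 window is 24 − t hours (4.1; 4.2 item 21) and a later day is 24 hours (4.3 item 15). With no change in rate and the totals used unscaled, ratio = 24/(24 − t).

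| Start | Day 1 hours | Ratio |
|---|---|---|
| 06:00 | 18 | 1.33 |
| 12:00 | 12 | 2.0 |
| 16:00 | 8 | 3.0 |
| 18:00 | 6 | 4.0 |
| 22:00 | 2 | 12.0 |

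The ratio reaches 2 when 24 − t ≤ 12, that is, for any start at or after 12:00, provided the infusion runs through one full later calendar day.

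**Loading bolus.** If Day 1 also holds a bolus worth b hours of infusion, the ratio is 24/(24 − t + b), which reaches 2 when t ≥ 12 + b. For b = 2 the threshold is 14:00; for b = 4 it is 16:00.

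**Rate change.** If the later rate is g times the Day 1 rate, a doubling is recorded when t ≥ 24 − 12g. A 25% rise is flagged for starts from 09:00, a 50% rise from 06:00. A 25% fall is still flagged for starts from 15:00.

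**Effect on incidence.** The protocol gives neither a start-time distribution nor the share of children with a full Day 2, so both are assumptions. Let p be the true incidence, f the share starting after noon and c the share on a full Day 2 at constant rate. Apparent incidence = p + (1 − p) × f × c, with no loading bolus.

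| p | f = 0.3, c = 0.5 | f = 0.5, c = 0.8 | f = 0.7, c = 1.0 |
|---|---|---|---|
| 0.25 | 0.25 + 0.75 × 0.15 = 36% | 0.25 + 0.75 × 0.40 = 55% | 0.25 + 0.75 × 0.70 = 78% |
| 0.10 | 0.10 + 0.90 × 0.15 = 24% | 0.10 + 0.90 × 0.40 = 46% | 0.10 + 0.90 × 0.70 = 73% |

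At p = 0.25 the smallest error is 11 points, more than twice the planned precision.

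**Does scaling by start time repair it?** Scaled baseline = (Day 1 dose / hours from Time 0 to midnight) × 24. For a flat infusion without boluses this returns the true 0-24 h dose at every start time, and the ratio is 1.0. With a bolus it does not. Take a 22:00 start, in units of one hour of infusion:

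- Bolus worth 2 h: Day 1 = 2 + 2 = 4; scaled = 4/2 × 24 = 48; true 0-24 h = 24 + 2 = 26; 48/26 = 1.85.
- Bolus worth 4 h: Day 1 = 2 + 4 = 6; scaled = 6/2 × 24 = 72; true = 24 + 4 = 28; 72/28 = 2.57.

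An inflated baseline hides real doublings, so the error changes direction but still depends on clock time.

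**The case against.** The strongest reply is that the protocol nowhere tells the analyst to use the to-midnight amount as the baseline. A reader might infer from the data elements that raw totals will be compared. The documents do not support that as a statement of the plan: every endpoint definition names the first 24 hours, and under it a constant infusion is not tolerance. Item 20 also records Time 0, so an hourly Day 1 rate can be derived, and an analysis plan not shown here may say so. This stands, and it makes the false doubling conditional on unscaled use.

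A reader might also infer that half of all children would be misclassified. That needs uniform start times, an unchanged rate through a full Day 2 for every child, and no loading bolus. None of these is documented. Data collection ends with the last opioid dose, death or PICU discharge, and item 21 includes boluses, so the true share could be well below half.

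Nor do the documents link start time to surgery or centre, so spurious risk factors of that kind are a possibility and not a finding. Cumulative dose and hours of exposure run from the first dose and are not affected by the midnight cut.

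What the reply does not remove is the gap in the data. An analysis plan can choose a formula, but it cannot separate the post-midnight part of the first 24 hours from a Day 2 total.

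**Conclusion.** The point holds as a mismatch inside the protocol: the endpoint's baseline is a 24-hour dose that the listed elements do not capture, and no conversion rule is stated.

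Its size depends on how the gap is handled. With unscaled totals, constant infusions started at or after 12:00 (14:00 or 16:00 with a bolus worth 2 or 4 hours) count as tolerance once a full later day is recorded. Under the assumed ranges, a true incidence of 25% would appear as about 36-78%, and a true 10% as about 24-73%. These are illustrations under stated assumptions and not forecasts. With scaling by Time 0, the artefact disappears for flat infusions. It remains, in either direction, when boluses are given or rates change, and is worst when Day 1 is short. Because the primary result is exposed and the remedy is small, it should be corrected before data collection closes.

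**What to change.** Add to Section 4.2 the total opioid dose, infusions plus boluses, from Time 0 to Time 0 + 24 h. Equivalently, add the amount from midnight to Time 0 + 24 h, to be summed with item 21. Use it as the baseline that Sections 1.3, 3.3, 4.1 and 5.1 already define; those definitions need no new baseline, only a pointer to the element that supplies it. State that it is compared with totals of equal length, such as consecutive 24-hour blocks from Time 0 or full calendar days. If calendar days are chosen, say how Study Day 2 is handled, since it overlaps the baseline window.

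If records are already closed, use Day 1 dose / hours from Time 0 to midnight × 24, with a sensitivity analysis taking Study Day 2 as baseline. In either case, do not treat the unscaled Day 1 total as a daily dose in the endpoint, the average daily dose or the trajectory analyses.

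The cost is one extra chart-derived total per child and a protocol amendment, which Section 4 requires for any added data element. No extra patients or procedures are needed.
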